9.2 Dose Modification

9.2.1 Previous embolization treatment

The calculated protocol dose of SIR-Spheres® microspheres can be modified. If patients have had prior trans-arterial embolization, then the calculated protocol dose will be decreased by 25%. The dose may also be decreased to limit the total radiation dose to the liver to 30 Gy.

9.2.2 Shunting to the lung

The percent lung shunting may alter the activity that can be safely implanted commensurate with an acceptable risk of radiation pneumonitis. The following recommendations apply:

Percent Lung Shunting Activity of SIR-Spheres® microspheres

<10%: Deliver full amount of SIR-Spheres® microspheres

10% to 15%: Reduce amount of SIR-Spheres® microspheres by 20%

15% to 20%: Reduce amount of SIR-Spheres® microspheres by 40%

>20%: Do not give SIR-Spheres® microspheres

The reduction in the activity implanted should be considered in light of the radiation dose that may be received by the tumor. In some patients, a reduction in activity of 20% may ensure the safety of the lung, but no longer provide sufficient radiation to the tumor. This will depend on the bulk of tumor being treated and the tumor to normal ratio of SIR-Spheres® microspheres deposition. This can be determined from the nuclear medicine breakthrough scan, in which the amount of MAA in the liver can be quantified into that in the tumor and that in the normal liver.

The final dose of individual treatment will be determined by a radiation oncologist based on the information described above.

10.0 Radiation Safety

Personnel involved in any aspect of handling SIR-Spheres® microspheres must be suitably qualified and be appropriately trained to deal specifically with this device. This includes nuclear medicine staff, staff involved in the implantation procedure and in post-implant care of the patient. Such staff requires the support of a radiation safety officer or expert in radiation physics, and licenses for the facility will normally require that such expertise is available to ensure safe use of isotopes within the facility. Complete information will be found in the Radiation section in the Sirtex Medical User Manual (Appendix 1).

Radiation exposure to the treatment team and to either nursing staff or visitors following the implantation is presented in depth in the Sirtex Medical User Manual. The representative exposure levels for the technician or pharmacist preparing a typical patient dose, and for the physician implanting that prepared dose of SIR-Spheres® microspheres are also included in this manual.

11.0 Safety Assessment

11.1 Definitions

11.1.1 Adverse Event (AE)

An AE is any untoward medical occurrence that happens during the specified medical event reporting period regardless of whether or not it is considered related to treatment.

AEs include the following:

- All suspected adverse medication reactions.
- All reactions from medication, overdose, abuse, withdrawal, sensitivity, or toxicity.
- Apparently unrelated illnesses, including the worsening of a preexisting illness (see Preexisting Conditions below).
- Injury or accidents. Note that if a medical condition is known to have caused the injury or accident (*e.g.*, a fall secondary to dizziness), the medical condition (dizziness) and the accident (fall) should be reported as two separate adverse events.
- Abnormalities in physiological testing or physical examination (findings that require clinical intervention or further investigation beyond ordering a repeat [confirmatory] test).
- Laboratory abnormalities that require clinical intervention or further investigation (beyond ordering a repeat [confirmatory] test) unless they are associated with an already reported clinical event.

Diagnostic and therapeutic non-invasive and invasive procedures, such as surgery, should not be reported as adverse events. However, the medical condition for which the procedure was performed should be reported if it meets the definition of an adverse event.

11.1.2 Preexisting Conditions

In this trial, a preexisting condition (*i.e.*, a disorder present before the adverse event reporting) should not be reported as an adverse event unless the condition worsens or episodes increase in frequency during the adverse event reporting period. Recurrence or progression of tumor will not be regarded as an adverse event, but will be recorded for patient follow-up.

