1.8 SIRT for metastatic uveal melanoma

Radioactive plaque and proton beam radiation have been used for treatment of primary uveal melanoma. Although melanoma cells are generally resistant to radiation, treatment of metastatic uveal melanoma with high-dose local radiation might have therapeutic benefits. In our institution, a total of 12 uveal melanoma patients, five men and 7 women, ages 48-81 (median 65) with hepatic metastases were treated with SIRT due to tumor progression after trans-arterial embolization (n=9), complications of trans-arterial embolization (n=1) or patient preference (n=2) (32). Patients had both hepatic lobes treated on separate occasions (n=7), one lobe (n=3) or whole liver (n=2) therapy. Treatment dose per patient was reduced by 25% due to prior trans-arterial embolization procedures. The mean total SIRT dose delivered was 1.0 GBq (0.62-1.47 GBq). Five patients had

an increase in hepatic enzymes (Grade1-4) at 1-month follow-up. No procedure related deaths or serious adverse events were experienced. Best tumor response was as follows: CR (n=0), PR (n=0), SD (n=8), PD (n=4), with a median follow-up of 7.8 months (1.0-16.0). The median time to liver progression was 7.0 months (1.0-15.5). Nine of the 12 patients, including 2 patients with >25% pretreatment tumor burden, died due to progression of liver disease (n=6), extrahepatic disease (n=1) or both (n=2). Post-SIRT, median overall patient survival was 10.8 months (1.0-19.0). Three patients (ECOG 0 performance status) are still alive at 13.5-19.0 months (median 16.2 months) following SIRT. Although this is a small retrospective study at a single institution conducted in heavily pre-treated patients, the potential efficacy of radiosphere treatment in metastatic uveal melanoma was suggested. Our observation is supported by a report from other institutions (33) and warrants further investigation in a prospective clinical study. In this clinical trial, we will prospectively investigate the safety and efficacy of SIRT using yttrium-90 SIR-Spheres® microspheres in uveal melanoma patients with hepatic metastases. Patients will be stratified based on their history of previous transarterial embolization of the hepatic artery. The safety and efficacy of treatments will be separately analyzed in these two patient cohorts.

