2.0 Study Objectives and Endpoints

2.1 Study Objectives

2.11 Primary Objectives

- (1) Investigate the potential efficacy (clinical response) of radioactive yttrium⁹⁰ microspheres in hepatic metastasis from uveal melanoma.
- (2) Investigate the safety of radioactive yttrium⁹⁰ microsphere in patients with metastatic uveal melanoma.

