2.2 Study Endpoints

- (1) Response Rate: 60% stabilization rate (CR+ PR+SD) warrants future study.

(2) Adverse Events: Treatment-emergent and related serious adverse events, and Grade 3 and 4 laboratory abnormalities for safety assessments.

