The development of acute peptic ulceration is suggested by the recognized symptoms of ulcer disease and diagnosed by endoscopy. If this were to occur, the patient should be treated using best standard practice, including pain relief, gastric acid blocking drugs and intravenous fluids.

Treatment is the same as for any cause of acute peptic ulceration.

Delayed Serious Events

Radiation Pneumonitis

Microsphere shunting to the lungs can cause edema and fibrosis that may not be reversible. Extrahepatic shunting may be identified through the injection of ^{99m}Tc -MAA into the hepatic artery (20, 21). High levels of implanted radiation and/or excessive shunting to the lung may lead to radiation pneumonitis. This may be suspected if patients develop a non-productive cough several days or weeks after the implantation of SIR-Spheres® microspheres and is diagnosed by chest X-ray. Patients should be treated with systemic corticosteroids and supportive care until symptoms have subsided.

Radiation Hepatitis

The use of radiosphere leads to irradiation of both tumor and normal liver parenchyma. As a result, patients with diseases which compromise the functioning of the liver parenchyma or with very small lesions scattered throughout the normal parenchyma may be at greater risk of liver function impairment. Excessive radiation to the normal liver parenchyma may result in radiation hepatitis. This can be difficult to diagnose, and may appear many weeks after the implantation of SIR-Spheres® microspheres. It is suspected if there is unexplained progressive deterioration in liver function. The diagnosis can be confirmed by histological examination of core liver biopsy. If the diagnosis is suspected or proven then patients should be treated with systemic corticosteroids and supportive care until the inflammation settles.

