11.1.3 Adverse Event Reporting Period

The adverse event reporting period for this trial begins when the patient receives the first radiosphere treatment and ends 3 months after the last radiosphere treatment. All adverse events that occur in trial subjects during the adverse event reporting period specified in the protocol will be reported, whether or not the event is considered treatment-related.

In addition, even after the completion of adverse event reporting period, if investigators consider that patients develop a serious adverse event that would be possibly related to the study treatment, such SAE will be reported.

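### Clinical liver failure or death ascribed to liver progression can be left out of the related serious-event count; the laboratory component and all-cause collection narrow this gap but do not close it

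*Combined protocol and SAP*

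**What the plan says.** Section 2.11 makes safety the second primary objective. Section 2.2 defines its endpoint as "Treatment-emergent and related serious adverse events, and Grade 3 and 4 laboratory abnormalities for safety assessments". The laboratory part carries no relatedness condition.

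Section 11.1.2 states: "Recurrence or progression of tumor will not be regarded as an adverse event, but will be recorded for patient follow-up". It does not say what evidence of progression is needed, or whether the clinical consequences of progression are excluded along with the progression itself.

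On collection, Section 11.1.3 says that adverse events from the first treatment until 3 months after the last "will be reported, whether or not the event is considered treatment-related". Beyond that window, "if investigators consider that patients develop a serious adverse event that would be possibly related to the study treatment, such SAE will be reported". The Protocol Summary (Duration of Follow-up) gives a different end: 3 months, the start of another locoregional or systemic treatment for progression, or death, whichever is first.

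Section 11.3 has one of the investigators attribute each event. Section 3.0 describes the trial as open-label and uncontrolled.

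On radiation hepatitis, Section 8.4 says: "This can be difficult to diagnose, and may appear many weeks after the implantation". It is to be suspected when liver function worsens without explanation. Biopsy is named as a means of confirmation, not as a requirement.

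**The concern.** Every patient in this trial has liver metastases, so tumour progression is a ready explanation for worsening liver function. Section 8.4 makes the absence of an explanation the trigger for suspecting radiation injury. The two diagnoses can look alike at the bedside, there is no control arm to show the background rate, and no independent review is described.

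If a radiation-caused liver failure or death is put down to tumour, it is not a related serious event and so falls outside that part of the Section 2.2 endpoint. At stake is how completely the trial reports liver injury, a delayed serious toxicity that Section 8.4 itself names.

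**Working it through.** **The plan's own figures.** The plan states no figure for the safety endpoint. The group size of 24 comes from the efficacy design in Section 12.0 (stop at 3 or fewer of 8; negative at 10 or fewer of 24). An exact binomial calculation reproduces that design: power 0.8063 (stated 80.6%), and early-stop probability 0.806 at a 30% rate (stated 0.81) and 0.174 at 60% (stated 0.17). None of this bears on safety.

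**Where an event ascribed to progression goes.** This reads Section 2.2 as serious events that are both treatment-emergent and related.

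| Event | Collected? | Related serious event? | Laboratory component? |
|---|---|---|---|
| Grade 3–4 bilirubin or transaminase rise in the window | Yes (5.4) | No | Yes |
| New ascites or encephalopathy in the window, recorded as an adverse event | Yes (11.1.1, 11.1.3) | No | Only if laboratory values also reach Grade 3–4 |
| The same, recorded only as progression on a broad reading of 11.1.2 | For follow-up only | No | As above |
| Death while on study | Yes, serious-event form (5.9, item 7) | No | A death is not a laboratory value, though earlier values may count |
| Serious liver event after the window | Only if judged possibly related (11.1.3) | No | Bloods are drawn quarterly (5.7), but the plan does not say whether these values count |
| Event within 3 months but after another treatment for progression starts | Yes under 11.1.3, no under the Protocol Summary | No | Depends on which cut-off applies |

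The first row is closed by the laboratory component. The others are closed only in part.

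**Can progression be called without measured growth?** Table 1 in Section 7.1.4 rests on imaging. Section 7.2, however, lets hepatic progression be confirmed by physical examination, and Section 7.1.4 classes unconfirmed stable disease as progression. Section 11.1.2 does not say which sense it uses.

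**Size per event.** One recoded case moves a full group by 1/24 = 4.2 percentage points. As an illustration only, take 3 true events of which 2 are ascribed to tumour (exact Clopper-Pearson 95% intervals):

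- 3/24 = 12.5% (2.7% to 32.4%)
- 1/24 = 4.2% (0.1% to 21.1%)

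**Chance of counting at least one event.** Let p be the true rate of treatment-caused clinical liver failure and m the share ascribed to progression. Both are assumptions; the documents give neither. With n = 24, P(at least one counted) = 1 − (1 − p(1 − m))^24. For p = 0.10 and m = 0 this is 1 − 0.90^24 = 92%; for m = 0.5 it is 1 − 0.95^24 = 71%.

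| p | m = 0 | m = 0.25 | m = 0.50 | m = 0.75 |
|---|---|---|---|---|
| 5% | 71% | 60% | 46% | 26% |
| 10% | 92% | 85% | 71% | 46% |
| 15% | 98% | 94% | 85% | 60% |

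These figures apply only to events that the laboratory component does not also pick up.

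**The centre's own series (Section 1.8).** Of 12 patients, 9 died: 6 of liver progression, 1 of extrahepatic disease and 2 of both. So 6 + 2 = 8 of 9 deaths were ascribed wholly or partly to the liver tumour. Five of 12 patients had enzyme rises at 1 month, and no procedure-related deaths or serious events were recorded. This shows how often the attribution has to be made, not that it was wrong.

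**The case against.** The case against is substantial, and most of it stands.

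- A reader might infer that only related serious events count towards safety. Section 2.2 does not support this: Grade 3 and 4 laboratory abnormalities are a separate component without a relatedness condition, and Section 5.4 has liver tests every 2 weeks for a month and then monthly for three months. The wording can also be read as all treatment-emergent events plus related serious ones, which would narrow the gap further. Section 12.0 promises toxicity rates with intervals and sets no attribution filter.
- A reader might infer that Section 11.1.2 removes ascites, encephalopathy or liver failure from adverse events. It names progression, not its consequences. Symptomatic liver failure is excluded at entry (4.205), so its later appearance would be new and would meet the definition in Section 11.1.1.
- Deaths are not lost from collection. Section 5.9 requires a form whatever the cause, and Sections 11.4 and 11.5 send unrelated fatal events to the IRB and the DSMB. Patients already withdrawn for progression may, however, no longer count as participating.
- A reader might infer that the error must favour the device. That is plausible but not shown. The attribution scale has a possible category, and an investigator who knows the treatment could also label true progression as possibly related.
- The series in Section 1.8 is small and retrospective, with follow-up to 19 months. Its causes of death say little about events within 3 months of treatment.

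What remains is that these safeguards govern collection and reporting. They do not place a clinical event judged unrelated into the related serious-event count.

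**Conclusion.** The concern holds in a limited form. The related serious-event component depends on one investigator's unblinded attribution. Without a rule for separating radiation liver injury from progression, clinical liver failure or death ascribed to tumour can drop out of it. The laboratory component and the collection of events regardless of attribution limit the gap without closing it. The weakest points are clinical events and deaths judged unrelated, events after the 3-month window, and patients who start another treatment for progression.

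The size is unknown. It is 4.2 points per recoded case in a group of 24; the illustrated shift and the detection probabilities rest on assumed rates. Because the plan has no safety threshold, no planned decision would be reversed. What is affected is how complete the reported safety result is. The documents do not show that misclassification will occur, or in which direction. This is an inexpensive improvement worth making, not a defect that invalidates the safety assessment.

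**What to change.** - **Sections 2.2 and 12.0:** make the main safety result all treatment-emergent serious events and all clinical liver events (ascites, encephalopathy, liver failure, liver-related admission or death), regardless of attribution. Show the related subset beside it, and flag events where an already scheduled scan shows liver progression. This also settles the two readings of Section 2.2.
- **Section 11.1.2:** state that the exclusion covers radiological progression itself, not its clinical consequences.
- **Protocol Summary and Section 11.1.3:** reconcile the end of safety collection, since only the Summary ends it when another treatment for progression starts.

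The scan finding should be a flag, not a ground for exclusion. Dropping events with scan-shown progression would contradict counting regardless of attribution. Table 1 also covers only treated lobes, and Section 7.1.3 does not treat new lesions in untreated lobes as progression.

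The cost is revised wording, an amendment through the IRB (Section 14.2) and one more table. Within the Section 11.1.3 window, events of any attribution are already collected, and no extra scans are needed. Later non-fatal events remain collected only if judged possibly related, and the table should say so. The downside is that the reported liver event rate will include some true disease events and look higher.

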11.1.3 Adverse Event Reporting Period

The adverse event reporting period for this trial begins when the patient receives the first radiosphere treatment and ends 3 months after the last radiosphere treatment. All adverse events that occur in trial subjects during the adverse event reporting period specified in the protocol will be reported, whether or not the event is considered treatment-related.

In addition, even after the completion of adverse event reporting period, if investigators consider that patients develop a serious adverse event that would be possibly related to the study treatment, such SAE will be reported.

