TIME	Within 4 weeks prior to enrollment	Within 6 weeks prior to treatment	Within 4 weeks prior to treatment	Within 4 weeks prior to treatment	Within 4 weeks prior to treatment	Day 0	Every 2 weeks	3-5 weeks after Initial Treatment	Every 2 weeks	1 month after the last treatment	3 months after the last treatment	6, 9, 12, 15, 18, 21, 24 months after the last treatment	
Informed consent	X												
Demographics	X												
Medical history	X				X(*4)			X		X	X	X	X
Physical exam	X				X(*4)			X		X	X	X	X
Performance status	X				X(*4)			X		X	X	X	X
Concomitant medications	X				X(*4)			X		X	X	X	X
Dose calculation					X								
Order SIR-Spheres microspheres					X								
CBC, differential, platelets	X				X(*4)	X	X	X	X	X	X	X	X
PT, PTT, and INR	X				X			X					
Serum biochemistry (*1)	X				X(*4)	X	X	X	X	X	X	X	X
LDH	X				X(*4)	X	X	X	X	X	X	X	X
Pregnancy test (*2)	X				X(*4)								
Study blood drawing						X(*3)				X(*3)	X(*3)		
Liver tumor biopsy			X										
CT scan of chest, abdomen and pelvis	X				X(*4)					X	X	X	X
MRI of abdomen	X				X(*4)						X	X	X
PET scan					X						X	X	X
Volumetric measurement					X								
Hepatic angiogram				X		X		X					
Tc-99 MAA study				X									
Treatment with SIR-Spheres microspheres						X		X					
Toxicities & adverse events					X(*4)	X	X	X	X	X	X	X	X

*1: Comprehensive metabolic panel including total bilirubin, SGOT (AST), SGPT (ALT), alkaline phosphatase, albumin, creatinine, BUN, glucose, calcium

*2: For females of childbearing potential.

*3: 100 ml blood for peripheral blood mononuclear cells, and 10 ml of blood for serum collection.

*4: Tests can be skipped if screening evaluation is performed within 4 weeks prior to scheduled treatment.

*5: If necessary.

*6: Exit visit can be skipped if follow-up visit is performed within 4 weeks.

1.0Background

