3.0 Study Design

This is an open-label, uncontrolled single institution phase II study for metastatic uveal melanoma. Uveal melanoma patients who received one or less prior trans-arterial embolization treatment of hepatic metastasis are eligible. Patients will be stratified into two groups: Group A, no prior intra-hepatic arterial treatment, n=24; Group B, one prior hepatic trans-arterial embolization treatment, n=24. They will be treated with intra-hepatic arterial infusion of Yttrium-90 radioactive microspheres (SIR-Spheres® microspheres).

Within 4 weeks prior to radiosphere treatment, patients undergo the pre-assessment angiogram and technetium-99m-labelled macroaggregated albumin (^{99m}Tc -MAA) nuclear scan to block the collateral flow to non-target organs and to calculate the shunting rate to the lung. Once patients meet the eligibility criteria of the study, the radiosphere treatment will be given. The Yttrium-90 radioactive microsphere treatment generally consists of two sequential uni-lobar treatments, approximately 4 weeks (3 to 5 weeks) apart. In selected patients, if clinically feasible, a biopsy of hepatic metastasis will be obtained prior to radiosphere treatment to investigate the correlation between efficacy of treatments and molecular characteristics of metastatic uveal melanoma.

The side effects of Yttrium-90 radioactive microspheres will be monitored every 2 weeks for one month following each treatment and then every month for three months after the last radiosphere treatment. The efficacy of radiosphere treatment will be evaluated every 3 months from the last treatment for 2 years until disease progression or death.

If patients experience grade 3 toxicity after the first treatment with Yttrium-90 radioactive microspheres, the second radiosphere treatment will be held until the resolution of toxicity to grade 1 or less or for a maximum of 6 weeks. The dose of the second radiosphere treatment will be decreased by 50% for liver-related grade 3 toxicity. A dose reduction will not be considered for

grade 3 GI toxicity unless the next treatment is repeated to the same hepatic lobe. The study treatment will be discontinued for grade 4 toxicity or if patients do not recover from the grade 3 toxicity to at least a grade 1 within 6 weeks.

The study will require two years of accrual with an additional two years of follow-up for survival analysis.

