5.2 Flow study (therapy-planning angiography) and pretreatment assessment

Within 4 weeks of radiosphere treatment, therapy planning arteriography of the superior mesenteric and celiac arteries will be performed.

The major purpose of the flow study is as follows:

- 1) Confirm the ability to selectively catheterize the hepatic arterial vasculature.
- 2) Assess the flow characteristics in the hepatic arteries.
- 3) Determine the hepatic arterial supply to the tumor, i.e., right, left or both hepatic arteries.

- 4) Determine the influence of hepatic arterial anatomy relative to the intrahepatic distribution of tumor on the ability to treat the diseased portion of the liver as a single unilobar treatment, or two sequential unilobar treatments, or 2 fractionated whole liver treatments.
- 5) Confirm the absence of significant, uncorrectable blood shunting from the liver to the gastrointestinal tract or other abdominal organs (e.g., pancreas).
- 6) Perform a technetium-99m macro-aggregated albumin (99m Tc-MAA) study to assess the presence and degree of lung shunting of the microspheres from the liver.

During the therapy planning angiography, selective arteriography of the proper, right and left hepatic arteries will be obtained in at least two projections (i.e. PA, RAO) to look for extrahepatic arterial blood supply arising from the hepatic arteries. Coil embolization of extrahepatic arteries (i.e. right gastric, gastroduodenal artery) will be performed as deemed necessary by the interventional radiologist performing the study. Following coil embolization of extrahepatic arteries, 99m Tc-MAA particles will be injected into the proper hepatic artery or injected separately into right and left hepatic arteries by splitting the 99m Tc-MAA dose. The injection location of 99m Tc-MAA will also be at the discretion of the interventional radiologist performing the procedure. The patient will be transported to nuclear medicine for a single photon emission CT (SPECT) scan to assess for shunting to the lungs and extrahepatic activity. CT scan of chest, abdomen, and pelvis with and without contrast, MRI of the abdomen with and without gadolinium, and PET scan will be performed as baseline imaging tests for radiosphere treatment. These tests will be done within 4 weeks of radiosphere treatment.

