5.3 Biopsy of hepatic metastasis

Within 4 weeks of radiosphere treatment, tumor specimens will be obtained by core biopsy of a representative hepatic metastasis. DNA as well as RNA will be extracted from the core biopsy specimens after confirming diagnosis of metastatic melanoma by histology and will be used for molecular studies including DNA array analysis and genome-wide SNP analysis. If patients have established diagnosis of metastatic uveal melanoma to the liver, they could decline this biopsy.

The tumor biopsy will also be exempt if the tumor tissue specimen can not be obtained by a conventional technique such as US-guided or CT-guided biopsy.

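### Adverse event reporting opens only at the first infusion, so non-fatal complications of the protocol's own pre-infusion procedures need not be recorded as adverse events

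*Combined protocol and SAP*

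**What the plan says.** Three parts of Section 11.1 decide what is recorded.

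- Section 11.1.3 sets the start: "The adverse event reporting period for this trial begins when the patient receives the first radiosphere treatment". The period closes 3 months after the last treatment. The only extension is forward in time, for possibly related serious events after the close (also in Section 11.2).
- Section 11.1.1 ties the definition to that period: "An AE is any untoward medical occurrence that happens during the specified medical event reporting period".
- Section 11.1.2 says that a disorder present beforehand "should not be reported as an adverse event unless the condition worsens or episodes increase in frequency during the adverse event reporting period".

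The procedures that come before the first infusion are these.

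- The flow study (Section 5.2) is scheduled once eligibility is confirmed (Section 5.1) and done within 4 weeks of treatment. It comprises superior mesenteric and celiac arteriography and MAA injection, and "Coil embolization of extrahepatic arteries (i.e. right gastric, gastroduodenal artery) will be performed as deemed necessary by the interventional radiologist performing the study".
- The biopsy (Section 5.3): "Within 4 weeks of radiosphere treatment, tumor specimens will be obtained by core biopsy of a representative hepatic metastasis". Section 3.0 limits it to selected patients in whom it is feasible and gives its purpose: "a biopsy of hepatic metastasis will be obtained prior to radiosphere treatment to investigate the correlation between efficacy of treatments and molecular characteristics". Section 5.3 lets patients with an established diagnosis decline it.

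Two provisions reach back before the first infusion. Section 5.9 requires an SAE form for any death during participation, whatever the cause. The schedule table in the Protocol Summary marks toxicities and adverse events at the pretreatment assessment, but with footnote *4, which reads: "4: Tests can be skipped if screening evaluation is performed within 4 weeks prior to scheduled treatment".

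**The concern.** Safety is one of the two primary objectives (Section 2.11). The flow study is invasive and nobody is infused without it. The biopsy serves the molecular research aims. Harm from either is harm that patients meet because they are in the trial, yet the reporting rules start after both are over.

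Two consequences follow. First, the reporting tables in Section 11.4 require grade 4 events to be reported whatever their attribution, but those tables work on adverse events as Section 11.1.1 defines them, and a work-up complication before the first infusion falls outside that definition. Second, Sections 4.202 and 4.203 exclude patients whose MAA scan shows lung shunting above 20% or whose major collaterals cannot be closed. Those facts are known only after the flow study, so these patients have had the angiogram, and perhaps coils, but their reporting period never opens. The same holds for anyone too unwell after the work-up to be infused.

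**Working it through.** **1. Timing.** The schedule table places enrolment within 6 weeks before treatment, and biopsy, flow study and pretreatment assessment each within 4 weeks before treatment. The uncovered procedural window is therefore up to 4 weeks; the 6 weeks belong to enrolment.

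**2. Sections 11.1.1 to 11.1.3 applied to a work-up complication.**

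| Complication of flow study or biopsy | Adverse event as written? |
|---|---|
| Non-fatal, resolved before first infusion | No: outside the period |
| Non-fatal, present and stable at first infusion | No: preexisting |
| Present at first infusion, then worse or more frequent | Yes |
| First appears after first infusion | Yes, until 3 months after the last treatment |
| Non-fatal, patient never infused | No: period never opens |
| Fatal | SAE form under Section 5.9 |

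**3. The schedule entry.** The adverse-event row is blank under screening, enrolment, biopsy and flow study. Its first mark is the pretreatment one with footnote *4. The skip is conditional: it applies only if screening fell within 4 weeks of scheduled treatment. Screening may be up to 4 weeks before enrolment and enrolment up to 6 weeks before treatment, so screening can be as early as 4 + 6 = 10 weeks before treatment, and many patients may not qualify for the skip. For those who do, the screening visit cannot stand in for the check: it has no adverse-event entry, and the flow study is scheduled only after eligibility is confirmed. Where the check is done, what it finds is still not an adverse event under Sections 11.1.1 and 11.1.3. The table and Section 11.1.3 are not aligned.

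**4. Size.** The plan gives no work-up complication rate, so there is no figure of its own to reproduce on this point. The figure that bears on exposure is the stage I stopping probability in Section 12.0, which does reproduce. At a true rate of 30%, the sum over x = 0 to 3 of C(8,x) × 0.3^x × 0.7^(8−x) is 0.0576 + 0.1977 + 0.2965 + 0.2541 = 0.806 (stated 0.81). At 60% it is 0.174 (stated 0.17). If both groups stop at stage I, 8 + 8 = 16 patients are exposed rather than 24 + 24 = 48.

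With n patients having the work-up and an assumed per-patient complication rate q, the expected number is n × q and the chance of at least one is 1 − (1 − q)^n.

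| Assumed q | n = 48: expected | n = 48: at least one | n = 16: expected | n = 16: at least one |
|---|---|---|---|---|
| 1% | 0.5 | 38% | 0.16 | 15% |
| 2% | 1.0 | 62% | 0.32 | 28% |
| 5% | 2.4 | 91% | 0.8 | 56% |
| 10% | 4.8 | 99% | 1.6 | 81% |

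For example, 48 × 0.05 = 2.4 and 1 − 0.95^48 = 0.91. These are events that occur. Those missed are fewer, because rows 3, 4 and 6 of the first table are captured. In the other direction, the documents do not say whether patients excluded after the flow study count towards the 48; if they do not, more than 48 have the work-up.

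**The case against.** The strongest reply is that the window suits the stated aim. The objective is the safety of the microspheres, and the endpoint in Section 2.2 is serious events that are treatment-emergent and related, plus grade 3 and 4 laboratory abnormalities. A period opening at first treatment matches that. A reader might infer that the reported safety endpoint is biased downward. The documents do not support this: the risk of the whole treatment pathway is not a stated endpoint, and work-up events would lie outside the treatment-emergent endpoint even with a longer window. The gap is in the capture of work-up harm.

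A reader might also infer that a patient harmed in the work-up leaves no trace, or that serious work-up events escape all expedited reporting. Neither is supported. Section 5.9 covers deaths. Section 14.2 obliges the investigator to inform the IRB of events reportable under local rules. Sections 11.4 and 11.5 defer to an institutional monitoring plan that is not in the documents. The FDA route in Section 11.4 is limited to events associated with treatment, so an earlier start would not by itself send procedural complications there.

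It is also fair to say that coils are placed only as needed, that the biopsy is selective, and that it is unclear whether an adverse-event check is one of the tests that footnote *4 allows to be skipped. All of this narrows the point. None of it makes a non-fatal complication confined to the pre-infusion weeks an adverse event under Section 11.1, and none of it opens the period for a patient who is never infused.

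**Conclusion.** The point holds as a gap in safety capture. Non-fatal complications of the planning angiogram (with MAA injection and any coils) in every patient who reaches it, and of the biopsy in those who have one, are not adverse events unless they appear or worsen after the first infusion. Patients excluded on the flow-study result are not covered at all, short of death. The Section 5.9 rule and the schedule entry soften this without moving the start of the period.

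The conclusion rests on the text and needs no assumed rate. The size does: over 1% to 10% in 48 patients, the expected number of complications runs from 0.5 to 4.8. That range is illustrative, an upper bound on what 48 patients' work-up would leave unrecorded at each rate, and smaller if a group stops at stage I. Sample size, type I error and power are unaffected. This is a change that should be made because it is cheap and safety is a primary objective; it is not a flaw that invalidates the design.

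**What to change.** - In Section 11.1.3, open the AE and SAE reporting period at the first study-specific invasive procedure (biopsy or flow study, whichever comes first) for every enrolled patient, including those never infused. State when the period ends for the never-infused, since the present end is counted from the last treatment.
- Bring Sections 11.1.1 and 11.1.2 into line, so that a complication of a study procedure is not classed as preexisting.
- In the schedule table, remove footnote *4 from the toxicity and adverse-event row. Entries under the biopsy and flow-study columns would cover patients who go no further.
- Tabulate pre-infusion procedure-related events separately, with all patients who underwent a procedure as the denominator. Leave the Section 2.2 treatment-emergent endpoint unchanged, so that post-infusion toxicity stays distinct.

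The cost is a few more adverse event forms and one extra table, with no change to the sample size or the efficacy analysis.
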